#### Participants discontinuing study treatment due to PD:

Imaging for disease assessment will stop and participants will enter the safety and survival follow-up.

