## 6.8 Treatment Beyond Progression

Participants may continue to be treated with the scheduled regimen and dose assigned at the discretion of the Investigator until one of the following criteria is met:

- Disease progression based on the Modified Lugano criteria assessed by the Investigator or pathological progression confirmed by biopsy. The assessment of PD must be confirmed by a repeat evaluation made by PET.
- Any of the study intervention discontinuation criteria is met.
- Clinical symptoms or signs indicating clinically significant PD such that the benefit-risk ratio of continuing therapy is no longer justified based on Investigator judgment.
- Decline in ECOG performance status compared to baseline.
- Rapid PD or threat to vital organs/critical anatomical sites (eg, spinal cord compression) requiring urgent alternative medical intervention, and/or continuation of study therapy would prevent institution of such intervention.

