# 9.4.2.2 Secondary Endpoint(s) Duration of Response

The DoR is defined as the time from the date of first documented response, assessed by Investigator for Part A and by BICR for Cohorts B1 and B2, using the Modified Lugano criteria, until the date of documented progression or death due to any cause (in the absence of disease progression). The end of response should coincide with date of progression or death from any cause used for the PFS endpoint. The time of the initial response will be defined as the latest of the dates contributing towards the first visit that was CR or PR.

The analysis will include all participants in the response-evaluable analysis set who had a response, regardless of whether the participant withdraws from therapy.

If a participant does not progress following a response, then the DoR will use the PFS censoring time.

Kaplan-Meier plots of DoR will be presented if data permitted. Median DoR, including 95% CIs, will also be presented, calculated from the Kaplan-Meier curve. In addition, the number of participants still responding at 3, 6, and 12 months after initial response will also be presented. Swimmer plots that clearly show the profile of each participant who responds will also be produced.

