#### **Progression-free Survival**

PFS is defined as the time from first dose until the earlier of the date of first documented disease progression, per Lugano classification as assessed by the Investigator for Part A (by BICR for Cohorts B1 and B2), or death (by any cause in the absence of disease progression or subsequent anticancer treatment). Participants who have not progressed or died at the time of analysis, or have unknown status, will be censored at the time of the latest date of assessment from their last evaluable assessment. Additional information and supportive/sensitivity analyses will be provided in the SAP.

The PFS time will always be derived, based on scan/assessment dates, not visit dates.

Disease assessments/scans contributing toward a particular visit may be performed on different dates. The following rules will be applied:

- Date of progression will be determined, based on the earliest of the dates of the component that triggered the progression.
- When censoring a participant for PFS, the participant will be censored at the latest of the dates contributing to a particular overall visit assessment.

Kaplan-Meier plots of PFS will be presented. Summaries of the number and percentage of participants experiencing a PFS event, and type of event (progression or death) will be provided along with the median PFS, its 95% CI and the proportion of participants who were progression free at 3, 6, 12, 18, and 24 months.

The treatment status at progression of participants at the time of the analysis will be summarized. This will include the number and percentage of participants who were on treatment at the time progression, the number and percentage of participants who discontinued study intervention prior to progression, the number and percentage of participants who have not progressed and were on treatment or discontinued treatment. This will also provide a distribution of number days prior to progression for participants who have discontinued treatment.

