4.2.6.2 Derivations

PFS (months) = (date of PFS event [progression/death] or censoring – date of first dose + 1) / (365.25/12).

Participants who have not progressed or died at the time of analysis, or have unknown status, are censored at the time of the latest date of assessment from their last evaluable disease assessment. However, if the participant progresses or dies immediately after two or more consecutive missed visits, the participant is censored at the time of the latest evaluable disease assessment prior to the two missed visits. Note: a NE visit is not considered as a missed visit.

If the participant has no evaluable disease assessments post-baseline or does not have baseline tumor assessment data they are censored at Day 1, unless they die within 57 weeks (i.e, 2 missed visit after Year 1 whereby disease assessments are every 6 months [2 x 26 weeks + 5 week for late visit = 57 weeks]) then the death qualifies as a PFS event. Participants who are censored at Day 1 are included in the FAS and the analysis but they do not contribute to any risk set. For participants who met one or more censoring conditions, PFS will be censored according to the earliest censoring condition; for participants who met none of the censoring conditions, PFS will be calculated by the earliest PFS event date.

A summary of censoring rules and the date of PD/death or censoring are given in Table 4.

Note that censoring overrides event in certain specified cases.

Table 4 Summary of Censoring Rules for PFS

Situation	Date of PD/Death or Censoring	PFS Outcome
Documented Progressive Disease (PD) or death in the absence of progression	Date of earliest documentation of PD or date of death	Event
Either no assessment at baseline or no evaluable assessments post-baseline AND death prior to Year 1 scheduled post-baseline disease assessment	Date of death	Event
Either no assessment at baseline or no evaluable assessments post-baseline AND no death prior to Year 1 scheduled post-baseline disease assessment	Date of first dose (Day 1)	Censored
PD or death (in the absence of progression) 57 weeks since previous disease assessments	Last evaluable progression-free disease assessment prior to missed assessments	Censored
At least one post-baseline tumor assessment, On- going with neither PD nor death at the time of analysis or lost to follow-up or withdrawn consent	Date of last evaluable disease assessment	Censored

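### In Part B, imaging stops at an Investigator progression call that BICR need not share, so BICR-scored PFS, DoR and DoCR are open to informative censoring that no planned analysis isolates

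*Protocol*

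**What the plan says.** **Who scores the endpoint.** Protocol 9.4.2.2 defines PFS progression "per Lugano classification as assessed by the Investigator for Part A (by BICR for Cohorts B1 and B2"). DoR is "assessed by Investigator for Part A and by BICR for Cohorts B1 and B2, using the Modified Lugano criteria", and DoCR follows the same split. SAP 4.2.4 to 4.2.6 agree. Cohort B1 also includes Part A participants treated at the RP2D, whose images BICR reads retrospectively (note to SAP Table 2).

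**Who ends the imaging.** Protocol 6.8 ends treatment on "Disease progression based on the Modified Lugano criteria assessed by the Investigator or pathological progression confirmed by biopsy". It adds: "The assessment of PD must be confirmed by a repeat evaluation made by PET". Protocol 7.1 lists progression confirmed by PET-CT as a reason to discontinue. For participants who discontinue for progression it says: "Imaging for disease assessment will stop and participants will enter the safety and survival follow-up". Protocol 7.1 does not name the assessor; the link to the Investigator comes from 6.8. Protocol 8.1.3 sends all Part B scans to BICR, unscheduled ones included, but does not make the end of imaging depend on the BICR reading.

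**What happens to the data.** SAP 4.2.6.2: "Participants who have not progressed or died at the time of analysis, or have unknown status, are censored" at their last evaluable disease assessment. SAP Table 4 censors at the last evaluable assessment before any new anticancer therapy. It treats a death as an event only up to 57 weeks after the previous assessment. For DoR, the protocol says: "If a participant does not progress following a response, then the DoR will use the PFS censoring time". SAP 4.2.5.2 does the same for DoCR.

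**What else is planned.** SAP 4.2.4.4, 4.2.5.4 and 4.2.6.4 repeat the Part B analyses with Investigator responses throughout.

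**The concern.** One assessor decides when follow-up by imaging ends, and another decides whether an event has occurred. When the two disagree in one direction (Investigator progression, BICR not), BICR gets no later scan and the participant leaves the risk set. Kaplan-Meier treats that participant as having the same outlook as those still followed. A participant the treating physician has just judged to be progressing probably has a worse one.

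At stake are the Part B secondary endpoints PFS, with its 12- and 24-month landmarks, DoR and DoCR. The study has no randomized comparator, so a shift in these absolute estimates is not offset by an equal shift in a control arm.

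**Working it through.** **1. The plan's own figure.** The 57-week limit in SAP 4.2.6.2 is two six-monthly intervals plus 5 weeks for a late visit: 2 × 26 + 5 = 57. It reproduces.

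**2. Paths for a participant with Investigator progression that BICR did not call on that scan.**
- BICR calls progression on the confirming PET: event.
- No BICR progression, new therapy starts: censored at the last evaluable scan before it.
- No BICR progression, death within 57 weeks and before new therapy: event at death.
- No BICR progression and neither of these, or a later death: censored at the last evaluable scan.

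The second and fourth paths create the problem.

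**3. Inputs for the size.** The documents give no discordance rate and no expected PFS, and the on-treatment scan cycles are redacted, so all of these are assumptions: exponential PFS with median 6 or 12 months; scans at weeks 12, 24, 36 and 52, then every 26 weeks; a share d of BICR progressions called by the Investigator one scan earlier; 0% or 30% of discordant participants dying within 57 weeks without new therapy.

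**4. Hand calculation (median 12 months = 52 weeks, no such deaths).** The chance of progressing in an interval of w weeks is h = 1 − 2^(−w/52): 0.1478 for 12 weeks, 0.1921 for 16 and 0.2929 for 26. At each scan after the first, a share d of the events leaves the risk set one scan early. The Kaplan-Meier factor changes from (1 − h) to (1 − h)/(1 − d·h), so

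- 12-month PFS as planned = 0.50 / [(1 − 0.1478d)² (1 − 0.1921d)]
- 24-month PFS as planned = 0.25 / [(1 − 0.1478d)² (1 − 0.1921d) (1 − 0.2929d)²]

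| d | 12-month, imaging continued | 12-month, as planned | 24-month, imaging continued | 24-month, as planned |
|---|---|---|---|---|
| 10% | 0.500 | 0.50/0.9520 = 0.525 | 0.250 | 0.25/0.8971 = 0.279 |
| 20% | 0.500 | 0.50/0.9056 = 0.552 | 0.250 | 0.25/0.8026 = 0.311 |
| 30% | 0.500 | 0.50/0.8607 = 0.581 | 0.250 | 0.25/0.7160 = 0.349 |

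**5. Simulation (200,000 participants per setting).** Over both medians and both death shares, the shifts in percentage points were:

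| d | 12 months | 24 months |
|---|---|---|
| 10% | +2.4 to +2.6 | +1.1 to +2.9 |
| 20% | +4.9 to +5.3 | +2.3 to +6.2 |
| 30% | +7.6 to +8.3 | +3.7 to +9.8 |

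**6. If the Investigator's call does not predict later BICR progression.** The difference is about 0.1 point at most with no qualifying deaths. With 30% qualifying deaths it runs from +0.8 to −0.6 points at 12 months and from −0.2 to −3.9 points at 24 months.

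**7. If the repeat PET gives BICR a further look.** With scans at about 2, 5, 8 and 12 months and 20% discordance, the 12-month shift was +5.5 points. If a repeat PET two months later let BICR call progression in half of the discordant cases, it fell to +2.7; if in three quarters, to +1.3. These resolution rates and the two-month gap are assumed.

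**8. Scale.** For a 12-month rate near 0.50 and n = 100, the approximate maximum for Cohort B1 in Protocol 9.2, the binomial standard error is √(0.5 × 0.5/100) = 0.05, or 5 points. DoR and DoCR were not simulated; the same mechanism reaches them through the shared censoring date.

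**The case against.** The strongest reply is that the plan already limits the problem. Progression must be confirmed by repeat PET, suspected pseudo-progression is rescanned at least 4 weeks later, and unscheduled scans go to BICR, so BICR often gets another look before imaging ends. Deaths within 57 weeks and before new therapy remain events. Investigator-based PFS, DoR and DoCR are planned. SAP 4.2.6.3 breaks PFS down by type of event or censoring and reports treatment status at progression; SAP 4.2.4.3 and 4.2.5.3 tabulate censoring reasons. No hypothesis is tested, and the futility and No-Go rules use ORR and CRR only.

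Most of this stands, and it limits size and importance. It does not close the gap. BICR need not agree with the confirmed call. Participants judged to be progressing are likely to start new therapy, which removes the protection of the death rule. The Investigator-based analysis replaces the assessor for every participant, so a gap between the two curves mixes reading differences with the effect of censoring. The participants at issue appear in the planned summaries but cannot be picked out, because SAP Table 4 has no category for them. Protocol 9.4.2.2 refers to the SAP for PFS supportive and sensitivity analyses; SAP 4.2.6 contains only the Investigator-based one.

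A reader might infer that every such participant is censored and that Part B PFS is certainly overstated. The documents do not support that. Some will die as events, some will be called by BICR on the repeat PET, and the direction depends on whether the Investigator's call predicts BICR progression, which cannot be known from the documents.

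**Conclusion.** The concern holds as a risk of informative censoring. The assessor mismatch and the absence of a targeted analysis are plain in the text. An upward bias in BICR-scored PFS, DoR and DoCR is the probable direction but is not established.

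Under 10 to 30% discordance with BICR progression one scan later, 12-month PFS rises by about 3 to 8 points. At 20% that is about one standard error for n = 100. The figure rests wholly on the assumed discordance, scan times and median, and on every discordant participant progressing by BICR at the next scan. Partial resolution by repeat PET reduces it; calls that carry no information bring it to about zero or below. Because the endpoints are secondary and descriptive, no error rate or sample size is affected and no specified decision rule uses them. What is affected is how far the 12- and 24-month landmarks can be taken at face value.

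**What to change.** Add to SAP 4.2.4, 4.2.5 and 4.2.6 a Part B sensitivity analysis. It keeps BICR progression wherever it exists. Where BICR has not called progression and no later BICR-readable scan exists, it counts Investigator progression as the event, on the date of that scan. Add a row to the censoring-reason summaries for Investigator PD without BICR PD, so that the number of participants concerned is reported.

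Present the result as a lower bound. Each of these events is placed at the earliest date it could have been seen, and Investigator false positives become events, so the analysis errs downward. That is its downside, and the SAP should say so. The main BICR analysis stays as it is.

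The cost is one extra analysis for each of the three endpoints and one table row, using Investigator responses already in the eCRF and BICR readings already planned. It needs no added scans and no change to participant management.

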#### Participants discontinuing study treatment while in response (PR/CR) or with SD:

Participants will enter the safety follow-up and will carry on with efficacy assessments by imaging until PD, start of a new anti-cHL therapy or EoS, whichever comes first (Table 4 and Table 16).

Note:

- Radiotherapy administered alone after the last dose of sabestomig while a participant is in CR, with a consolidation intent will not be considered as a new anti-cHL line of therapy. Therefore, the participant should carry on the efficacy follow-up and perform disease assessment by imaging as per SoA (Table 16).
- Participant in CR/PR who proceeds to HSCT without any treatment between the last dose of sabestomig and the start of the conditioning regimen will be followed-up for disease assessment post-transplant as per SoC and data on their disease status will be collected in the EDC as part of the survival follow-up.

See the SoA (Table 1, Table 2, Table 3, and Table 4) for data to be collected at the time of discontinuation of study intervention and follow-up and for any further evaluations that need to be completed.

If the participant does not agree to continue in-person study visits, a modified follow-up must be arranged to ensure the collection of endpoints and safety information. This could be a telephone contact with the participant, a contact with a relative or treating physician, or information from medical records. The approach taken should be recorded in the medical records. A participant who agrees to modified follow-up is not considered to have withdrawn consent or to have withdrawn from the study.

All participants in Safety or Survival follow-up at the time of final study DCO will be contacted by the study site prior to the final study DCO to confirm their survival status and to inform participants that this was the last study-related contact, and no further survival data will be collected in respect to the study. Sites are requested to document this last contact in the source records.

## 7.2 Participant Withdrawal from the Study

• A participant may withdraw from the study at any time at their own request, or may be withdrawn at any time at the discretion of the Investigator for safety, behavioral, compliance, or administrative reasons. This is expected to be uncommon.

- A participant who considers withdrawing from the study must be informed by the Investigator about modified follow-up options (eg, telephone contact, a contact with a relative or treating physician, or information from medical records). If a participant agrees to modified follow-up options, the participant will not be considered to have withdrawn from the study (see Section 7.1).
- At the time of withdrawal from the study, if possible, an EoT visit should be conducted, as shown in the SoA. See the SoA (Table 4) for data to be collected at the time of the EoT Visit.
- If the participant withdraws consent for disclosure of future information, AstraZeneca may retain and continue to use any data collected before such a withdrawal of consent.
- If a participant withdraws from the study, it should be confirmed if they still agree for existing samples to be used in line with the original consent. If they request withdrawal of consent for use of samples, destruction of any samples taken and not tested should be carried out in line with what was stated in the informed consent and local regulation. The Investigator must document the decision on use of existing samples in the site study records and inform the Global Study Team.

## 7.3 Lost to Follow-up

A participant will be considered lost to follow-up if the participant repeatedly fails to return for scheduled visits and is unable to be contacted by the study site.

The following actions must be taken if a participant fails to return to the clinic for a required study visit:

- The site must attempt to contact the participant and reschedule the missed visit as soon as possible and counsel the participant on the importance of maintaining the assigned visit schedule and ascertain whether or not the participant wishes to and/or should continue in the study.
- Before a participant is deemed lost to follow-up, the Investigator or designee must make every effort to regain contact with the participant (where possible, 3 telephone calls and, if necessary, a certified letter to the participant's last known mailing address or local equivalent methods). These contact attempts should be documented in the participant's medical record.
- Should the participant continue to be unreachable, the participant will be considered to have withdrawn from the study.

Site personnel, or an independent third-party, will attempt to collect the vital status of the participant within legal and ethical boundaries for all participants who received any dose of study intervention. Public sources may be searched for vital status information. If vital status is determined as deceased, this will be documented, and the participant will not be considered lost to follow-up. AstraZeneca personnel will not be involved in any attempts to collect vital status information.

Discontinuation of specific sites or of the study as a whole are handled as part of Appendix A.

## 8. STUDY ASSESSMENTS AND PROCEDURES

- Study procedures and their timing are summarized in the SoA (Table 1, Table 2, Table 3, and Table 4). Protocol waivers or exemptions are not allowed.
- Immediate safety concerns should be discussed with AstraZeneca immediately upon occurrence or awareness to determine if the participant should continue or discontinue study intervention.
- AstraZeneca will continue to supply sabestomig in the continued access phase of the study (ie, PTAP) if the participant provides consent and while the participant is benefiting from the treatment, in the opinion of the investigator and in agreement with the medical monitor (see Section 6.9 and Section 8.9 for further details).
- Adherence to the study design requirements, including those specified in the SoA (Table 1, Table 2, Table 3, and Table 4), is essential and required for study conduct.
- All screening evaluations must be completed and reviewed to confirm that potential participants meet all eligibility criteria. The Investigator will maintain a screening log to record details of all participants screened and to confirm eligibility or record reasons for screening failure, as applicable.
  - Retesting of laboratory values during the screening period is allowed.
- Procedures conducted as part of the participant's routine clinical management (eg, blood count and imaging assessments) and obtained before signing of the ICF, may be utilized for screening or baseline purposes provided the procedures met the protocol-specified criteria and were performed within the time frame defined in the SoA (Table 1, Table 2, Table 3, and Table 4).

A total of approximately 110 mL of blood will be required for all screening tests, which will be conducted during the 28-day screening period. No more than approximately 300 mL of blood will be collected between Days 1 and 21 after the first dose of study intervention within any cohort. No more than approximately 100 mL of blood will be drawn on any visit day after Cycle 1. The total volume to be collected will depend on the number of doses administered and the length of follow-up.

## 8.1 Disease Response Assessment

Sites will be required to store electronic copies of all scans, and AstraZeneca will arrange for centralized storage of all imaging data. All imaging assessments, including unscheduled visit scans, will be collected on an ongoing basis and sent to AstraZeneca or designee for storage. The centralized storage of imaging data would allow independent centralized third-party blinded review of disease assessments. In this regard, and at the discretion of AstraZeneca, an independent central review of all scans used in disease assessment guidelines for imaging collection and storage will be provided in a separate document.

Participants will be evaluated by the Investigator for disease response using the Modified Lugano and RECIL criteria as secondary endpoints. Additionally, in Part B only, disease response will be evaluated by a BICR using Modified Lugano criteria. All participants will be followed up to evaluate OS. In the Part A of the study, imaging must be archived and transferred to the BICR to allow retrospective disease response assessment in participants treated at RP2D.

Efficacy assessments will be performed until PD/relapse, death, lost to follow-up, start of new treatment for cHL or withdrawal of the consent (whichever comes first). For participants discontinuing the study intervention due to other causes (eg, due to toxicities), disease follow-up will continue as per SoA until PD/relapse or start of new treatment for cHL is documented.

In the event pseudo progression is suspected by imaging, a PET-CT scan should be repeated at least 4 weeks after the previous assessment to confirm progression or response (Section 6.7) provided that the participants' clinical condition is stable. However, repeat imaging must be performed earlier than the next 12-week assessment where there is clinical suspicion of progression. The assessment of "clinically stable" must meet the following criteria:

- Absence of signs and symptoms (including worsening of laboratory values) indicating disease progression.
- No decline in ECOG performance status.
- Absence of rapid progression of disease.
- Absence of progressive tumor at critical anatomical sites (eg, cord compression) requiring urgent alternative medical attention.

Radiological response should be integrated with clinical data and pathological findings, where available. Regardless of the radiological response, new or worsening of clinical findings indicative of lymphoma progression will result in an overall response of PD.

Unless unequivocally attributed to the disease, whenever possible the presence of a new lesion should be confirmed by biopsy. Biopsies at PD/relapse are not mandatory but recommended. If clinically indicated, unscheduled assessments can be performed at any time during the study.

